Significant improvements in HbA1C have been shown in youth with type 1 diabetes with public insurance with uninterrupted CGM use.²² This real-world data in youth with type 1 diabetes has complimented research study data and paved the way for earlier and easier CGM approval for youth, particularly publicly insured youth.

Our team has shown that youth with T1D with public insurance who have uninterrupted CGM use compared to those who lose CGM coverage due to insurance issues have significant improvements in HbA1c^{22,23}. This real-world data in youth with T1D has complimented research study data and paved the way for earlier and easier CGM approval for youth, particularly publicly insured youth. We aim to translate these learnings to our T2D population. In our clinic, youth with T2D have a mean HbA1c of 8.6% with only 35% at goal HbA1c of <7% (n=311 HbA1c values), indicating that the majority of youth with T2D are not meeting this significant diabetes therapy goal. Reflective of the national data demonstrating youth with T2D are overwhelmingly minorities and from families of lower SES, a significant portion of our T2D patient population (n=131) is publicly insured (77%), minority status (73% and Latinx 66%), and has Spanish-speaking parents or guardians (56%), all groups which have lower rates of diabetes technology use^{11,24}.

Design: This will be a two-phase pilot program focused on youth with T2D to evaluate initiation and sustained use of CGM. The focus of phase 1 will be a feasibility trial to use CGM in 30 youth with T2D and public insurance over a 12-month period. CGM will be provided to all participants. Education for youth and their families about CGM integration in diabetes care will be provided throughout the study. Barriers to CGM adoptions and sustained CGM use will be tracked throughout this phase to inform the further refinement of the program in phase 2 in 50 youth with T2D. As part of closing the disparities in diabetes technology use in youth with T2D, QoL and PROs will be evaluated. The goals of phase 2 are to utilize human factors design data, QoL and PRO metrics collected in phase 1 to address identified needs and barriers to increase initiation and continued use of CGM in this population.

Inclusion criteria

1. Diagnosis of T2D (diabetes autoantibody negative) followed in the Pediatric Endocrinology clinic at Stanford Children's Health

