2. HbA1C greater than 6.5% at enrollment. This is to enroll patients who are working on improving glucose control but are still not meeting HbA1c targets.^{9,25}
3. Interested in starting on a continuous glucose monitor
4. Access to a mobile device that is compatible with CGM applications or willing to use CGM receiver which will be provided. Both the receiver and mobile device allows patients to view glucose data and alerts from the CGM and upload glucose data during or in between in-person or virtual clinic visits, not necessitating that the participant have access to a mobile device.
5. Public insurance
6. Age 4-20 years inclusive

Exclusion criteria

1. Non-T2D diagnosis
2. HgA1C < 6.5%
3. Participant not willing to wear CGM
4. Private insurance

Procedures and Methods

Recruitment: The study team will review clinic schedules to identify youth with T2D from the patients in our clinic who would qualify. The informed consent process will be conducted prior to initiating the study. Following CGM initiation by a CDE, youth will have a routine 1-week clinic follow up with our diabetes team and then will be seen per clinic standard of care, every 3 months thereafter for the 12 months of the study duration. At each visit we will collect descriptive data on CGM use, CGM glucose metrics, and provide CGM supplies. PROs will be evaluated at three time points during the study. In phase 2, we will identify a new cohort of eligible patients who will be evaluated at a similar cadence as phase 1.

Visit	1	2	2a	3	3a	4	4a	5	5a	6
Weeks from start	x	2 weeks	4-6 weeks	12 weeks						
Informed consent and assent Visit Type ** this will be modified if LibreView App is available during study duration, can move visits to TH with lab A1C	x (can be done in person or via TH)									
	In person	IP/TH	phone/IP	IP	phone/IP	IP	phone/IP	IP	phone/IP	IP
Demographics	x									
Diabetes History	x									
HbA1C	x			x		x		x		x
CGM start	x				x					x
PROs	x			x						x
CGM metrics	x	x	x	x		x		x		x
CGM education	x	x	x			x		x		x
CRC check on supplies (confirm use and shipment)	x	x	x	x	x	x	x	x	x	x
Final study visit										x

Visit 1:

- Participants will be offered the opportunity to start on CGM at their scheduled clinic visit
- Participants will receive CGM education from a certified diabetes educator (CDE)

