- The care team member initiating the CGM will ask patients and their caregivers if they are interested in hearing about this study to understand the use of CGM in youth with type 2 diabetes
- If a patient and/or caregiver is interested in this study, one of the study team members will discuss the study with the participant and obtain informed consent and assent (if needed).
- Participants who consent to be part of this study will have the appropriate CGM applications and readers active (Libre 2 CGM, LibreView, LibreLink) as per standard clinical care.

1. Informed consent and assent - this can be done in person or virtually
2. CGM start – done by CDE in clinic
 - a. 4 weeks of supplies given – CRC to confirm with family preferred way to get supplies every 6 weeks and best way to contact them.
 - b. Standard clinic CGM education
3. Routine clinic visit

4. PRO completion - participants who speak and write English and Spanish will be asked to complete PROs surveys

Visits 2a,3a,4a,5a:

1. CRC check in with family/patient
 - a. Confirm CGM use
 - b. Address CGM issues – CRC to address or forward to CDE if clinical question
 - c. Ship or arrange for supply pick up (6 weeks of supplies)
 - d. Confirm next clinic visit

Visits 2,3,4,5,6:

[figure not shown]
1. Routine Clinic visit including CDE visit. The purpose of these visits is to reinforce prior teaching, answer questions, and review CGM data, making changes as necessary to the patient's care regimen to better control their diabetes.
2. CRC check in, supplies provided (for all visits except visit 6)
3. PRO questionnaires administered for visits 3 and 6

Biostatistical plan

Statistical methods: We will generate descriptive statistics for all participants included in the study and will create a STROBE diagram²⁶ to describe participants screened, recruited, and followed in both study phases. To address the feasibility of CGM use in T2D, we will estimate the proportion of participants who have sustained CGM use in both phase 1 and 2. Our feasibility analysis will include all participants. To address H1c, we will fit linear regression models using GEE to estimate the association of PROs with longitudinal HbA1c. Logistic regression models fit with GEE will be used to estimate the association of PROs with dichotomous diabetes management outcomes (e.g., presence of diabetes distress).

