Problem Areas in Diabetes – Pediatric (Diabetes Burden)	Youth 8-17 and all parents	YOUTH – Youth will complete this survey on psychological distress and burden associated with taking care of diabetes. Child survey for 8-11 years, Teen survey for 12-17 years. PARENTS – complete a proxy version as well as a report of their own distress.
Use of and Comfort with Technology	Youth ≥ 11 , All parents	YOUTH – Youth ages 11-18 will complete this survey on use of and comfort with general technology and diabetes devices. PARENT – All parents complete the same questions on technology and devices.
PROMIS Global Health scale (PGH-7)	Youth ≥ 11	YOUTH – Youth will complete this survey on their overall health, integrating patient experiences across physical, mental and social health

Community Partnership and Engagement

Once complete, results from this study will be shared with medical leadership of California Children's Services (public insurance which provides coverage of diabetes-related care for our youth with type 2 diabetes) at the state and county level to advocate for coverage and access to CGM technology for all youth with type 2 diabetes. We will also engage with the Pediatric Endocrinology Family Advisory Counsel at Stanford Children's Health to combine results from this study with patient/parent advocacy efforts to gain insurance coverage for CGM in all youth with T2D.

Potential Pitfalls and Contingency Plans

Study participants are asked to attend clinic appointments as recommended by their care provider. Our clinic standard is to have patients attend at least 4 visit per year, on average 1 clinic visit every 3 months. There may be missed appointments. Efforts will be made to remind families of appointments the day before the visit by phone or MyChart messaging. If a patient misses an appointment, the team will make efforts to re-schedule the appointment and address barriers to attending clinic appointments.

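### Modelling diabetes distress as yes/no in logistic GEE, with no cut-off stated, gives up precision that the survey score would keep in cohorts of 30 and 50

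*Combined protocol and SAP*

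**What the plan says.** Under Biostatistical plan, Statistical methods, H1c is addressed by two sets of models. Linear GEE relates PROs to longitudinal HbA1c. For the second set, "Logistic regression models fit with GEE will be used to estimate the association of PROs with dichotomous diabetes management outcomes", with a single example in brackets: "e.g., presence of diabetes distress".

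The PRO survey table gives the instrument, Problem Areas in Diabetes – Pediatric: "Youth will complete this survey on psychological distress and burden associated with taking care of diabetes". The youth forms are age-limited: "Child survey for 8-11 years, Teen survey for 12-17 years". All parents complete a proxy version and a report of their own distress.

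The Design section sets phase 1 as a "feasibility trial to use CGM in 30 youth with T2D and public insurance over a 12-month period", followed by "further refinement of the program in phase 2 in 50 youth with T2D". The age criterion is "Age 4-20 years inclusive". PROs are collected at visits 1, 3 and 6.

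The documents do not give the number of items, score range, distress cut-off, expected prevalence, reason for dichotomising, significance level or target power. The one PRO threshold stated, 21 or lower on PROMIS Global Health (Data Collection and Entry), triggers a referral and belongs to a different scale.

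**The concern.** Presence of distress is not observed directly. It has to be made by cutting a survey measure. The cut treats participants just either side of it as opposites and everyone on one side as identical. In small cohorts that loss is felt most.

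Two features of this plan add to it. H1c expects distress to decline, which is a change in level; a yes/no outcome cannot register any change that stays on one side of the cut. And with child, teen, proxy and parent-own versions and no cut-off for any of them, the cut could be chosen after the data are seen.

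At stake is how precisely the association models can estimate anything about distress. The feasibility endpoint is not affected.

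**Working it through.** There is no power or precision figure in the plan to reproduce, so this check only sizes the loss.

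**From the documents:** cohorts of 30 and 50 (Design); three PRO assessments (visit schedule); baseline PROs as predictors (H1c in Specific Aims); logistic GEE (Statistical methods).

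**Assumed, because the documents are silent:** the survey yields a roughly normal score; the share p classed as distressed lies between 20% and 80%; two-sided 5% test; within-person correlation rho of the score between 0.4 and 0.8; complete data.

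**Step 1. One assessment.** The information in the cut score relative to the uncut score is φ(z_p)² / [p(1−p)], where φ is the normal density at the cut. It is the same for p and 1−p.

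| Cut | Relative information | Loss | 30 is worth | 50 is worth |
|---|---|---|---|---|
| 50/50 | 0.3989² / 0.25 = 0.637 | 36% | 19 | 32 |
| 30/70 | 0.3477² / 0.21 = 0.576 | 42% | 17 | 29 |
| 20/80 | 0.2800² / 0.16 = 0.490 | 51% | 15 | 25 (24.5) |

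The loss reaches 50% at about a 21/79 split and 66% at 10/90.

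**Step 2. Three assessments, predictor fixed at baseline.** Repeated yes/no values are less correlated within a person than the scores beneath them, so repetition recovers part of the loss. Relative information becomes (step 1 value) × (1 + 2·rho) / (1 + 2·phi_b), where phi_b is the within-person correlation of the binary outcome.

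| Cut | phi_b at rho 0.4 / 0.6 / 0.8 | Relative information | Loss |
|---|---|---|---|
| 50/50 | 0.262 / 0.410 / 0.590 | 0.752 / 0.770 / 0.759 | 23-25% |
| 30/70 | 0.248 / 0.394 / 0.577 | 0.693 / 0.708 / 0.695 | 29-31% |
| 20/80 | 0.226 / 0.370 / 0.556 | 0.607 / 0.619 / 0.603 | 38-40% |

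For example, 50/50 at rho 0.6 gives 0.637 × 2.2 / 1.82 = 0.770. Across the table, 30 participants are worth 30 × 0.603 = 18 to 30 × 0.770 = 23, and 50 are worth 30 to 38.5. If rho is close to 0 or to 1, the loss returns to about the step 1 values.

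**Step 3. Power under GEE.** This used 400 simulated trials per setting, three assessments, a residual within-person correlation of 0.6 and an exchangeable working correlation. It compared linear GEE on the score with logistic GEE on the cut score.

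| Setting | 50/50 | 30/70 | 20/80 |
|---|---|---|---|
| n=30, r=0.4: score vs yes/no | 80% vs 64% | 81% vs 63% | 76% vs 55% |
| n=50, r=0.3: score vs yes/no | 71% vs 60% | 74% vs 58% | 76% vs 52% |

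The cut does not enter the score analysis, so differences along a row in its power are simulation noise: the standard error is √(0.8 × 0.2 / 400) = 2 percentage points. As a cross-check at n=30 and 20/80, power of 75.5% corresponds to a noncentrality of 1.96 + 0.69 = 2.65. Multiplying by √0.619 = 0.787 gives 2.085, and Φ(2.085 − 1.96) = 55%, in line with the simulation. The correlations of 0.4 and 0.3 are illustrative.

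**Step 4. Who contributes.** Enrolment runs from 4 to 20 years, but the youth distress survey covers 8 to 17, so youth-reported numbers may fall below 30 and 50. Parent report covers every family. The plan does not say whether the phases are pooled (30 + 50 = 80).

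**The case against.** The strongest reply is that the plan does not say distress will be analysed only as yes/no. It is given as an example. The same section applies mixed-effects modelling to the trajectory of measured variables, and Specific Aims lists PROs among the measured outcomes, so the uncut score may well be modelled there. This stands in part. The mixed-model sentence does not name the PROs and describes trajectories. In the association analysis, the only form in which distress is named as an outcome is dichotomous; the linear GEE has HbA1c as its outcome.

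A second reply is that screening positive has a use here, since out-of-range PRO scores trigger a psychosocial response. That supports reporting the percentage. It does not require regressing on it, and no distress cut-off is given.

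A third is that this is a pilot with no power claim. That is right, and it limits the point to precision.

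Three stronger readings are tempting, and the documents do not support them:

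- A reader might infer that the planned analysis loses a third to a half of the information. That range is for one normally distributed assessment with roughly 21-79% distressed; the plan has three.
- A reader might infer that a cohort of 30 leaves only 6-9 events (20-30% of 30). That counts one visit. Three visits give up to 18-27 correlated event-visits before missing data, and pooling the phases is not excluded.
- A reader might extend the criticism to CGM use. Statistical methods does not name CGM use as a logistic outcome. The proportion with sustained use is the endpoint of H1a and H1b, and days of wear are separately related to time in range.

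**Conclusion.** The point holds in a limited form. The plan names distress as a yes/no outcome for logistic GEE and gives neither a cut-off nor a reason. With a roughly normal score and 20-80% classed as distressed, the loss is about 36-51% for one assessment. For three assessments with a baseline predictor and rho of 0.4-0.8, it is about 23-40%. In the n=30 simulation this cost roughly 16 to 21 percentage points of power (80 − 64 = 16; 76 − 55 = 21). A rarer or more common category would lose more, and a strongly skewed score would change the figures.

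No stated figure is wrong, and H1c as a whole is not undermined: its HbA1c models and its expected decline in distress do not depend on this logistic model. What is lost is precision in one secondary association analysis, and the loss is avoidable with data already being collected.

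**What to change.** In Statistical methods, state that where distress is the outcome in the association analysis, the Problem Areas in Diabetes – Pediatric score at visits 1, 3 and 6 will be modelled on its own scale, by linear GEE or the mixed model already planned. Say which report is used (youth, parent proxy or parents' own distress), how the child and teen forms are combined, and whether the phases are pooled. Report presence of distress only as a descriptive percentage at each visit, with the cut-off for each form fixed and justified before the data are analysed.

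The cost is a few sentences and no new data. The small downside is that results are expressed in score points instead of odds of screening positive; the descriptive percentages keep the screening view available. The sustained-use proportions should stay as they are.

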We propose a pilot and feasibility trial to use continuous glucose monitoring (CGM) in youth with type 2 diabetes (T2D) and public insurance. This feasibility trial would fill a gap in the literature with respect to CGM use in youth with type 2 diabetes. The findings from this trial can provide much needed data to pave the way for future studies using CGM technology in this population. Our proposal is focused on youth with public insurance, seeking to provide diabetes technology for patients and their families to use in daily diabetes management. This pilot is an expansion of our existing program of CGM access to youth with type 1 diabetes which has led to an improvement HbA1C of 0.5% over 1 year and positive feedback from patients and families.^{1,2}

Specific Aim 1: Evaluate the feasibility of CGM start and continuation in youth with T2D and describe glucose metrics and patient reported outcomes (PROs). We will pilot and refine a program to test the hypothesis that CGM start and continuation in youth with T2D is feasible and then evaluate glucose metrics and PROs.

Hypothesis 1a: In phase 1, CGM use exceeding >50% of participants will be feasible and sustainable in youth with T2D, measured by days of CGM use per 2-week period (>75%). **H1b:** Following an additional needs assessment after phase 1, in phase 2 sustained CGM use per 2-week period (>75%) will exceed 75% of participants. **H1c:** Based on completion of PROs surveys, it is expected that diabetes-specific distress will decline, and overall well-being/quality of life will improve. Secondary outcome PROs (see protocol synopsis) collected at baseline will be associated with HbA1c and diabetes management outcomes. Data on glucose metrics, SDOH, and needs and barriers will be described.

Specific Aim 2: To assess the clinical outcomes (HbA1C, time in range [70-180 mg/dL], time in hypoglycemia [<70 mg/dL]) of individuals participating in this trial compared to clinic historical controls.

Hypothesis 2: Use of CGM will improve HbA1C and other clinical metrics of diabetes glucose control.

Measured Outcomes:

1. Sustained use of CGM by patients over one year measured by days of CGM use per every 2-week period with >80% as goal.
2. Change in HbA1C over first year of CGM use
3. Glucose profile metrics: percentage time in range, time in hypoglycemia, and time in hyperglycemia obtained from CGM.
4. Change in weight and BMI over first year of CGM use using clinic visit weight and BMI measurements.
5. PROs

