At each visit we will collect descriptive data on CGM use, clinical glucose outcome metrics, and provide CGM supplies. Mixed affects modeling will be used to characterize the trajectory of measured variables and to account for patient-level correlation of this data. To account for gaps in CGM use we will use intention to treat analysis and consider a censoring method for a patient who leaves the practice or are lost to follow up. We will also perform an exploratory analysis of the relationship at a patient-level between days of CGM wear and time in range.

Study Timeline

Data Collection and Entry

1. Study participant data entry will be collected and entered in Stanford RedCap by the study team.
2. PRO will be collected in RedCap

The initial survey is filled out in person during the CGM visit during which, parents provide an email that will be the platform for contact for the future surveys. At the follow up points, the RedCap data base will automatically trigger survey link to the email on file. If the survey is not completed, a second email is sent as a reminder followed by provider team reminders. Participant data will be included for analysis for the time frames that are available when.

These measures will assess issues of adherence or illness distress and provide valuable information for providers to better understand the impact of early CGM initiation. The patient/guardian will have the option of filling out the questionnaires in English or Spanish. Based on the evidence in the PROs literature and our clinical experiences, we have developed an algorithm for responding to PROs screen scores that are outside of the normative range triggers a response from social worker and/or diabetes psychologist²⁷. Study personnel will complete a chart review to collect relevant health information including diagnosis, duration of disease, indicators of health status, and regimen information (e.g. medication, doses). These medical record data are required to assess the validity and usefulness of the clinical PROs screening measures. Additionally, reliability analysis will be conducted to examine the psychometric properties of the PROs measures, and the satisfaction questionnaire data will be aggregated to assess the acceptability of the PROs procedure from the patient's perspective.

- PROMIS global health (youth): BELOW 22 for the PROMIS global health scale. Anyone who scores 21 or lower would trigger an alert to place a diabetes psychology referral.

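### Intention to treat cannot account for gaps in CGM use in metrics that exist only on worn days; if non-wear is related to glucose within a participant, time in range can shift with no true change.

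*Combined protocol and SAP*

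**What the plan says.** - Biostatistical plan, Statistical methods: "To account for gaps in CGM use we will use intention to treat analysis". For participants who leave, the plan will only "consider a censoring method for a patient who leaves the practice or are lost to follow up"; no method is named, and this concerns departure rather than gaps in wear.
- Same section, longitudinal model: "Mixed affects modeling will be used to characterize the trajectory of measured variables". The random effects, covariates and missing-data assumption are not given.
- Measured Outcomes, item 3: "Glucose profile metrics: percentage time in range, time in hypoglycemia, and time in hyperglycemia obtained from CGM". Specific Aim 2 makes time in range and time below 70 mg/dL clinical outcomes alongside HbA1c, compared with historical clinic controls. Hypothesis 2 expects HbA1c and the other glucose metrics to improve.
- Statistical methods, last sentence: "We will also perform an exploratory analysis of the relationship at a patient-level between days of CGM wear and time in range".
- Data Collection and Entry: "Participant data will be included for analysis for the time frames that are available when". The sentence breaks off and stands in a paragraph about surveys, so whether it covers CGM data is unclear.
- Potential Pitfalls and Contingency Plans: a participant who stops CGM, or who misses more than 3 appointments, is withdrawn.

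Nowhere does the plan set a minimum wear for a time-in-range value to count, a rule for unworn days, or a sensitivity analysis for non-wear. The wear figures it does give (above 75% in Hypothesis 1a, above 80% in Measured Outcomes) are feasibility targets.

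**The concern.** Intention to treat can deal with gaps in use for outcomes that are measurable whether or not the sensor is on: HbA1c, weight/BMI and PROs. For a CGM metric an unworn day has no value, whatever analysis set is declared. What the mixed model then describes is glucose while worn, and that differs from glucose over the year when wear depends on glucose.

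The protocol makes such dependence plausible, though it does not show it. Background and Significance links diabetes distress both to glycemic outcomes and to self-monitoring. Substantial non-wear is also compatible with success: Hypothesis 1a needs only just over half of participants to exceed 75% wear.

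The within-participant trajectory carries much of the weight for these metrics. The Background says youth with type 2 diabetes have had little or no access to CGM, so historical controls will have few time-in-range values, and participants start CGM at visit 1. A claim that time in range improved would rest largely on change during follow-up, the period in which wear may fall. The results are intended for public insurance leadership (Community Partnership and Engagement).

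**Working it through.** The documents give no time-in-range level, variance, expected wear decline or bias figure, so there is no figure of the plan's own to reproduce. From the documents come the sample sizes (30 in phase 1, 50 in phase 2), the 2-week period and the 75% threshold. Every other input below is an assumption.

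**Step 1: size of the shift.** Let *w* be the fraction of days worn and *d* the worn-day minus unworn-day mean time in range.

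True mean = *w* × worn + (1 − *w*) × (worn − *d*) = worn − (1 − *w*) × *d*.

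So worn = true + (1 − *w*) × *d*. With the true mean and *d* constant, spurious change = (*w* at start − *w* at end) × *d*.

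| Wear, start to end | *d* = 5 | *d* = 10 | *d* = 15 |
|---|---|---|---|
| 95% to 75% (0.20 × *d*) | +1.0 | +2.0 | +3.0 |
| 95% to 60% (0.35 × *d*) | +1.75 | +3.5 | +5.25 |

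With *d* = 0 the change is 0. With *d* negative (better days unworn) the sign reverses.

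**Step 2: the same effect built from a wear pattern.** Take a true mean of 55%, half good and half bad days, and 90% wear on good days.

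- Gap of 20 points between good (65%) and bad (45%) days, wear on bad days down to 30%, so overall wear 60%: (0.45 × 65 + 0.15 × 45) / 0.60 = 60.0, a bias of +5.0. Gaps of 10 and 30 points give +2.5 and +7.5.
- Wear falling equally on all days, from 90% to 50%: observed mean 55.0, bias 0.

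**Step 3: the feasibility threshold is no guard.** Eleven of 14 days is 78.6%, above 75%. With 7 good and 7 bad days and all 3 missed days bad, a 20-point gap gives (7 × 65 + 4 × 45) / 11 = 57.7, a bias of +2.7. Gaps of 10 and 30 points give +1.4 and +4.1.

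**Step 4: does the mixed model remove it?** Simulation of a random-intercept model of time in range on visit: 5 visits of 14 days, no true change, mean 55, between-participant SD 18, day SD 15, 100 replicates per setting.

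| Why wear falls | Mean estimated change, n = 30 / n = 50 | p < 0.05, n = 30 / n = 50 |
|---|---|---|
| At random, 90% to 50% | −0.1 / 0.0 | 6% / 5% |
| Linked to the participant's average, about 87% to 50% | −0.1 / −0.1 | 7% / 3% |
| Linked to that day's glucose, 87% to 50% | +4.3 / +4.4 | 96% / 100% |

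The model copes with random loss and with selection between participants on a stable average. It does not cope with selection of days within a participant. The exploratory wear and time-in-range analysis uses the same worn days, so it cannot correct this either.

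**The case against.** A reader might infer that declining wear by itself will inflate time in range. The documents do not support that, and Steps 1, 2 and 4 contradict it: non-wear must be related to glucose within the participant, and the direction depends on which days are missed. For time in hypoglycemia the direction is unknown.

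A reader might also infer that the plan claims intention to treat fills in missing glucose values. It does not say so. CGM is the intervention, so a gap in use is non-adherence, and keeping such participants in the analysis is the ordinary meaning of the term. That reading is fair, but it leaves the unworn days with no rule at all.

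Nor does the plan ignore wear. Days of use per 2-week period is the first measured outcome, an exploratory wear analysis is planned, and HbA1c, which does not depend on wear, is scheduled at visits 1, 3, 4, 5 and 6 and is named first in Hypothesis 2. This stands, and it makes the remedy cheap. None of these items, however, is linked to the time-in-range analysis as a check or a correction.

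Finally, the sizes are illustrative, and this is a pilot whose first aim is to describe glucose metrics. That stands as a limit on how strongly the point can be put. Aim 2 and Hypothesis 2 nevertheless go beyond description.

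**Conclusion.** The point holds in a conditional form. For the CGM glucose metrics, the stated remedy for gaps in use cannot do what it is named for, and the mixed model estimates a while-worn trajectory. If wear falls and non-wear is related to glucose within participants, time in range can move with no true change: upward if worse days go unworn, downward if better days do.

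On the assumed inputs of Step 1 the spurious rise is 1.0 to 5.3 points. These figures rest on a constant worn-unworn difference and on wear levels that the documents do not give. They show what is possible and do not predict what this study will find. The reassurance about selection between participants rests on a random-intercept model and stable participant averages; the plan does not specify its random effects.

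A related inconsistency needs settling. Withdrawing participants who stop CGM leaves it unclear whether intention to treat covers HbA1c for the very participants with the least wear.

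**What to change.** 1. Limit the intention-to-treat statement to HbA1c, weight/BMI and PROs.
2. Label time in range, hypoglycemia and hyperglycemia as while worn, and report them per 14-day period beside days worn.
3. State that the Hypothesis 2 conclusion rests on HbA1c, with the CGM metrics as supporting evidence.
4. Pre-specify one sensitivity analysis, for time in range only. Give unworn days the participant's worn-day value minus 0, 5, 10 and 15 points; for a period with no wear, apply the offset to the participant's model-predicted value. Report the offset at which any gain disappears, rather than judging against an undefined small offset. With a constant offset this is roughly the observed gain divided by the fall in wear: a 2.0-point gain with wear falling from 95% to 75% disappears at 2.0 / 0.20 = 10 points. The grid tests a claimed improvement in one direction and should not be carried over to hypoglycemia or hyperglycemia.
5. Reconcile Statistical methods with Potential Pitfalls by stating whether routine HbA1c values obtained after withdrawal enter the intention-to-treat analysis.

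The cost is plan wording, one extra analysis on wear and HbA1c data already scheduled for collection, and a slightly weaker time-in-range claim.
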